**Table 10-1 Categorical clinical signs**

Clinical Symptom	Scale	Tool/Endpoint
Facial Rubor(redness)	0=none, 1=mild, 2=moderate,3=severe	Photographic interpretation, Count & percent shifts from baseline
Supraclavicular and dorsal fat pads	0=none, 1=mild, 2=moderate,3=severe	Photographic interpretation, Count & percent shifts from baseline
Hirsutism	Sum area scores to total body score,	Photographic interpretation, Descriptive % change from baseline
Striae	0=none, 1=mild, 2=moderate,3=severe	Photographic interpretation, Count & percent shifts from baseline
Muscle strength	0= minimum, 3= maximum	Direct observation of ability to stand unaided. Descriptive % change from baseline

### **Assess the improvement of health-related quality of life.**

Descriptive statistics, including mean, median, standard deviation, minimum and maximum, will be presented to describe actual standardized scores and changes from baseline. Graphical display(s) of descriptive results will be produced.

#### **10.3.1 Safety objectives**

##### **10.3.1.1 Analysis set and grouping for the analyses**

For all safety analyses, the safety set will be used. Key safety analyses will be presented for patients who receive pasireotide in combination with cabergoline after they started receiving the combination therapy.

The overall observation period will be divided into three mutually exclusive segments:

1. pre-treatment period: from day of patient's informed consent to the day before first dose of study medication
2. on-treatment period: from day of first dose of study medication to 28 days after last dose of study medication
3. post-treatment period: starting at day 28+1 after last dose of study medication.

##### **10.3.1.2 Adverse events (AEs)**

Summary tables for adverse events (AEs) have to include only AEs that started or worsened during the on-treatment period, the **treatment-emergent** AEs. However, all safety data (including those from the pre and post-treatment periods) will be listed and those collected during the pre-treatment and post-treatment period are to be flagged.

The incidence of treatment-emergent adverse events (new or worsening from baseline) will be summarized by system organ class and or preferred term, severity (based on NCI-CTCAE v4.03 grades), type of adverse event, relation to study treatment. Similar summaries will also be produced for treatment-emergent AEs of special interest. The number and percentage of patients with at least one treatment-emergent Adverse Event of Special Interest will be reported.

Deaths reportable as SAEs and non-fatal serious adverse events will be listed by patient and tabulated by type of adverse event and treatment regimen.

Specific safety event categories (SEC) will be considered. Such categories consist of one or more well-defined safety events which are similar in nature and for which there is a specific clinical interest in connection with the study treatment(s).

For each specified SEC, number and percentage of patients with at least one event part of the SEC will be reported.

#### **10.3.1.3 Laboratory abnormalities**

For laboratory tests covered by the National Cancer Institute - Common Terminology Criteria for Adverse Events (CTCAE) version 4.0, the study's biostatistical and reporting team will grade laboratory data accordingly. For laboratory tests covered by CTCAE, NCI-CTCAE v4.03 a Grade 0 will be assigned for all non-missing values not graded as 1 or higher. Grade 5 will not be used.

For laboratory tests where grades are not defined by NCI-CTCAE v4.03, results will be graded by the low/normal/high classifications based on laboratory normal ranges.

The following summaries will be generated separately for hematology, biochemistry and urinary laboratory tests:

- shift tables using NCI-CTCAE v.4 grades to compare baseline to the worst on-treatment value
- for laboratory tests where NCI-CTCAE v4.03 grades are not defined, shift tables using the low/normal/high/(low and high) classification to compare baseline to the worst on-treatment value.
- listing of all laboratory data with values flagged to show the corresponding NCI-CTCAE v4.03 grades and the classifications relative to the laboratory normal ranges.

In addition to the above mentioned tables and listings, other exploratory analyses, for example figures plotting time course of raw or change in laboratory tests over time or box plots might be specified in the MAP and/or SAP.

#### **10.3.1.4 Other safety data**

##### **ECG**

ECG data will be summarized with:

- shift table baseline to worst on-treatment result for overall assessments
- listing of ECG evaluations for all patients with at least one abnormality.

##### **Vital signs**

Vital signs (supine BP, HR & temperature) reporting of results will include:

- shift table baseline to worst on-treatment result
- table with descriptive statistics at baseline, one or several post-baseline time points and change from baseline to this/these post-baseline time points.

### **Karnofsky performance status**

Results will be summarized by visit using counts and percentages of

- patients in each performance status category.

### **Gallbladder Ultrasound**

Gallbladder data at each visit will be summarized and listed.

#### **10.3.1.5 Tolerability**

Tolerability will be studied in terms of dose reduction or drug interruption due to an AE.

[REDACTED]

#### **10.3.1.7 Patient-reported outcomes**

The health-related quality of life will be assessed for patients using the Cushing QoL, a Cushing's disease specific validated scale, and SF-12L, a generic QOL scale. These patient-reported outcome (PRO) measures are included as secondary endpoint in order to assess the beneficial clinical consequences of pasireotide LAR on disease specific and general QOL. Changes from baseline in the above outcomes measurements will be compared. PRO analysis of study data will be conducted on the subset of patients with all measurements. This analysis will utilize the previously defined Minimal Important Difference for Cushing QoL as well as correlations between Cushing QoL and SF-12 and both PRO instruments with UFC response and signs and symptoms of disease.

[REDACTED]

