## **2 Rationale**

### **2.1 Study rationale and purpose**

The treatment of patients with CD requires a multimodality approach. One approach is represented by medical treatment. Pasireotide, the first pituitary-targeted medical therapy approved for patients with CD showed efficacy in a proportion of patients in the registration study [SOM230B2305]. Overall results from the pivotal study demonstrated that pasireotide has a favorable benefit/risk profile in Cushing's disease. However, it was noted that some 65% and 48% of the patients completed 6- and 12-month treatment, respectively. Apart from the very beginning of the study, the main reason for discontinuation was due to insufficient therapeutic effect.

Cabergoline is often used in this indication in order to decrease cortisol levels; the literature has shown evidence of short-term efficacy but the long-term treatment highlighted treatment escapes in many patients. Therefore, combining medical treatment modalities can be considered in order to improve patient outcome.

Taking into consideration that biochemical remission should be rapidly achieved to reverse morbidity and mortality, drugs can be combined to control cortisol production within an acceptable time frame. If biochemical remission has been accomplished, drug dosage may be decreased or one of the used drugs may be withdrawn. Second, combining drugs may allow for lower doses with concomitantly less adverse events. Third, combining drugs may have potentiating effects on ACTH secretion by corticotroph tumor cells. Because most corticotroph adenomas simultaneously express sst5 and D2, it can be anticipated that a combination of sst5- and D2-targeting drugs may have additive or synergistic effects on ACTH secretion. In vitro data indeed indicate synergism between sst and D2 that might increase therapeutic efficacy.

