### **10.3 Secondary objectives**

The secondary efficacy analysis will be performed on the FAS.

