## **10.5 Sample size calculation**

The sample size was designed for the estimate of the proportions of patients with a normalized mUFC at week 35 in patients who are pasireotide untreated at screening or patients treated with pasireotide at screening but still with uncontrolled mUFC.

With a sample size of 64 patients and assuming that the proportion of patients who attain a mUFC  $\leq 1.0 \times \text{ULN}$  at week 35 will be 34 %, derived from a weighted mean of the original assumed response rates for Group 1 (35%) and 2 (28%) and assuming that a maximum of 6 out of 64 patients (approx. 10 %) will be enrolled in Group 2, the precision of the response will be 12.8 % for the associated two-sided 95% CI considering a drop-out rate of 10%.

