6.5.2 Secondary efficacy evaluation

The secondary efficacy endpoints will be summarized for the FAS and EXTENSION FAS for parameters from baseline measurements over core phase to week 35 and extension phase from week 43 to final cutoff date at each scheduled assessment:

1. Actual and percentage change in mUFC from baseline to each scheduled visit when UFC is measured until the final cut-off date
2. Proportion of patients with normalized mUFC (i.e $\text{mUFC} \leq 1.0 \times \text{ULN}$) as assessed at each scheduled visit when UFC is measured until the final cut-off date
3. Proportion of patients, at each visit, who attained $\text{mUFC} \leq 1.0 \times \text{ULN}$ (controlled) or have at least 50% reduction (partially controlled) from baseline in mUFC as assessed at

each scheduled visit when UFC is measured until the final cut-off date

4. Duration of controlled or partially controlled response is defined as the period starting from the date of patient's first normalization ($mUFC \leq 1.0 \times ULN$) or at least 50% reduction from baseline up to the date when the patient's $mUFC > 1.0 \times ULN$ and the reduction from baseline falls to less than 50% from the first time until the final cut-off date

5. Actual and percentage changes from baseline, at each scheduled post baseline visit, in plasma ACTH and serum cortisol over visit time window until the final cut-off date

6. Actual and percentage change from baseline over visit time window in clinical symptoms of Cushing's disease: blood pressure, body mass index, waist circumference, fasting serum lipid profile, and weight until the final cut-off date

7. Change from baseline in clinical signs of Cushing's disease: facial until the final cut-off date

8. Rubor, supraventricular and dorsal fat pads, hirsutism, striae (via photographs) and muscle strength until the cut-off date

9. Change from baseline in standardized scores, as measured by the Cushing's QOL and SF-12v2 over time until the final cut-off date

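### The protocol restricts the quality-of-life analysis to an undefined subset with all measurements, against the FAS named elsewhere, and so risks an optimistic and less precise result

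*Protocol*

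**What the plan says.** Three places bear on which patients enter the QoL analysis.

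- **Protocol 10.3.1.7 (Patient-reported outcomes):** "PRO analysis of study data will be conducted on the subset of patients with all measurements". The same paragraph introduces the minimal-important-difference analysis for Cushing QoL and the correlations of the two instruments with each other, with UFC response, and with signs and symptoms. It does not say whether all measurements means all visits, all items, both instruments or all correlated variables. Nor does it say whether the core phase alone or both phases count.
- **Protocol 10.3 (Secondary objectives):** "The secondary efficacy analysis will be performed on the FAS". Under that heading, the health-related quality-of-life paragraph says that descriptive statistics "will be presented to describe actual standardized scores and changes from baseline". It states no completeness condition.
- **SAP 6.5.2:** "The secondary efficacy endpoints will be summarized for the FAS and EXTENSION FAS". Item 9 of the list is "Change from baseline in standardized scores, as measured by the Cushing's QOL and SF-12v2 over time until the final cut-off date". Again there is no completeness condition.

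The SAP text available has no analysis paragraph for QoL, although it has one for each of the other efficacy endpoints in the list. The missing-data rules in Protocol 10.2.3 and SAP 6.5.2 concern mUFC only.

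**The concern.** A rule that keeps only patients with every measurement discards observed scores from everyone else. This is harmless if missingness is unrelated to QoL, but here there is reason to think it is related. Protocol 2.1 reports that in the earlier pivotal study "some 65% and 48% of the patients completed 6- and 12-month treatment, respectively", and that after the very beginning of that study insufficient effect was the main reason for stopping. In this trial, Protocol 7.1.2.1 requires withdrawal for lack of efficacy and for unacceptable drug-related toxicity. Patients who leave for those reasons may well have improved less on QoL, and a mean over the remaining patients would then look better than the mean over all treated patients.

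The documents also allow two analysts to follow the plan and report different patients for the same secondary endpoint. One would use the FAS and the other the complete-data subset. For the minimal-important-difference and correlation analyses there is no competing statement, so the restriction stands alone.

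**Working it through.** **Plan's own figure.** The only design calculation concerns the primary endpoint, not QoL. Protocol 10.5 starts "With a sample size of 64 patients", assumes a 34% response, and gives a precision of 12.8% "considering a drop-out rate of 10" per cent. With 64 × 0.90 = 57.6, about 58 patients, the exact (Clopper-Pearson) half-width at 34% is 12.8%, so the figure reproduces. The Wald half-width would be 12.2%. This confirms only that the planners expected about 58 evaluable patients.

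**Inputs for the QoL check.**
- N = 64 (Protocol 10.5).
- Share with complete data, c: 0.90 (this trial's planned drop-out), or 0.65 and 0.48 (6- and 12-month completion in the earlier study, Protocol 2.1). The last two are assumptions for this trial. The 35-week core phase falls between those two time points.
- The documents give no QoL standard deviation, no QoL missingness rate and no difference in QoL change between patients with and without complete data. That difference, the gap (complete minus incomplete), is assumed to be 0.25, 0.5 or 1.0 SD.

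**Formulas.** Patients kept = 64 × c. Factor by which the confidence interval widens = 1/√c. Bias of the complete-data mean against the mean of all 64 = (1 − c) × gap.

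| c | Patients kept | CI factor | Bias, gap 0.25 SD | Bias, gap 0.5 SD | Bias, gap 1.0 SD |
|---|---|---|---|---|---|
| 0.90 | 57.6, about 58 | 1.05 | 0.03 SD | 0.05 SD | 0.10 SD |
| 0.65 | 41.6, about 42 | 1.24 | 0.09 SD | 0.18 SD | 0.35 SD |
| 0.48 | 30.7, about 31 | 1.44 | 0.13 SD | 0.26 SD | 0.52 SD |

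With a gap of zero the bias is zero, and with a negative gap it reverses.

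**Missed forms (illustration only).** If each patient still in the trial independently missed 5% of forms over 4 to 8 visits, the numbers kept would be:
- c = 0.90: 64 × 0.90 × 0.95⁴ = 46.9, and with 0.95⁸, 38.2.
- c = 0.65: 64 × 0.65 × 0.95⁴ = 33.9, and with 0.95⁸, 27.6.

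The 5% rate, the independence and the visit count are all assumptions. The QoL rows of the visit schedule were not readable in the text available, so the true number of QoL visits could not be checked.

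**Extension.** Entry depends on approval and reimbursement in each country (Protocol 4.1), and the SAP's exposure categories run to 263 weeks. If all measurements spans both phases, patients would drop out of the analysis for administrative reasons as well, and the number kept would be lower than in the table.

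**The case against.** A reader might infer that QoL will be analysed only in completers, that improvement is therefore overstated, and that about half the FAS is lost. The documents do not support any of these as stated.

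- **Population.** For change from baseline, Protocol 10.3 and SAP 6.5.2 point to the FAS, so the restriction is one of two conflicting instructions.
- **Only completers.** All measurements is undefined. It could mean patients with every variable needed for the correlations, which would be ordinary for that analysis. If it means every visit, it would also drop a completer who missed one form.
- **Direction.** The gap is unknown in sign and size. Protocol 7.1.2.1 also lists withdrawal of consent, loss to follow-up and administrative reasons. With an assumed response of 34%, many retained patients would be non-responders.
- **Half the FAS.** This needs the 65% completion rate and the assumed missed forms together (a loss of 47 to 57%). At the planned 10% drop-out the same missed forms lose about 27 to 40%. The 65% comes from an earlier pasireotide monotherapy study, whereas here cabergoline is added for uncontrolled patients.
- **Absence from the SAP.** The core-phase SAP of 27 March 2017 and SAP section 8.3.2 were not available. A QoL missing-data rule could sit there, although 8.3.2 is cited only for the primary endpoint.
- **Stakes.** The trial is single-arm and exploratory with no hypothesis test, and QoL is secondary. Interpretation is affected, but error rates are not.

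These points limit the claim without removing it. The restriction is current protocol text, it is undefined, and it contradicts two other sections. The paragraph also refers to pasireotide LAR and SF-12L, whereas the trial uses the s.c. form and SF-12v2, so it may not have been fitted to this study.

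**Conclusion.** The point holds as an unreconciled conflict over the QoL population, together with a complete-data rule that should not be the main rule. For change from baseline the documents name two populations. For the minimal-important-difference and correlation analyses they name only the restricted one.

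The loss of patients before missed forms ranges from 6 of 64 (planned drop-out) to about 22 of 64 (65% completion, assumed), with confidence intervals wider by a factor of 1.05 to 1.24. It would be greater if the extension counts. The risk of an optimistic result is plausible but not demonstrated. Over the assumed gaps it is 0.03 to 0.10 SD at 90% complete data and 0.09 to 0.35 SD at 65%. It is zero or reversed if patients with incomplete data improve as much or more. A firm statement that the analysis overstates improvement would need QoL data that the documents do not contain.

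**What to change.** 1. Remove the all-measurements restriction as the main rule in Protocol 10.3.1.7, and reconcile that section with Protocol 10.3 and SAP 6.5.2. Name the FAS as the QoL population, and the Extension FAS for the extension phase.
2. Use all available scores for change from baseline, minimal important difference and correlations. Include end-of-treatment values from early discontinuers where these are collected, since Protocol 7.1.2 asks for the end-of-treatment assessments in such patients.
3. Report the number of patients contributing at each visit.
4. Define all measurements, and keep that subset as a sensitivity analysis.
5. Consider a repeated-measures model with visit and baseline score. Observed-case summaries by visit, even on the FAS, would still reflect drop-out. The model uses partial records, but it relies on missingness being explained by the observed data.

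The cost is a small wording change in both documents and one standard model, with no new data. Protocol 12.1 requires a written amendment for the protocol text. The SAP dated 27 October 2019 is already an addendum made after database lock, to add a Karnofsky analysis that had been missed. A QoL paragraph could be added in the same way, but anything added after lock should be labelled post hoc.

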### **10.4 Interim analysis**

No formal interim analysis is planned for this study. If Novartis publishes interim data, details will be specified in the study's analysis plan. Interim analysis may be performed for regulatory purposes if deemed necessary.

[REDACTED]

However, an analysis of this trial will be performed at the end of the core phase, while the final analysis related to the overall phase, including the core and the extension phases, will be performed at the end of the extension phase after December 2019.

## **10.5 Sample size calculation**

The sample size was designed for the estimate of the proportions of patients with a normalized mUFC at week 35 in patients who are pasireotide untreated at screening or patients treated with pasireotide at screening but still with uncontrolled mUFC.

With a sample size of 64 patients and assuming that the proportion of patients who attain a mUFC  $\leq 1.0 \times \text{ULN}$  at week 35 will be 34 %, derived from a weighted mean of the original assumed response rates for Group 1 (35%) and 2 (28%) and assuming that a maximum of 6 out of 64 patients (approx. 10 %) will be enrolled in Group 2, the precision of the response will be 12.8 % for the associated two-sided 95% CI considering a drop-out rate of 10%.

# **11 Ethical considerations and administrative procedures**

## **11.1 Regulatory and ethical compliance**

This clinical study was designed, shall be implemented and reported in accordance with the ICH Harmonized Tripartite Guidelines for Good Clinical Practice, with applicable local regulations (including European Directive 2001/20/EC and US Code of Federal Regulations Title 21), and with the ethical principles laid down in the Declaration of Helsinki.

## **11.2 Responsibilities of the investigator and IRB/IEC/REB**

The protocol and the proposed informed consent form must be reviewed and approved by a properly constituted Institutional Review Board/Independent Ethics Committee/Research Ethics Board (IRB/IEC/REB) before study start. Prior to study start, the investigator is required to sign a protocol signature page confirming his/her agreement to conduct the study in accordance with these documents and all of the instructions and procedures found in this protocol and to give access to all relevant data and records to Novartis monitors, auditors, Novartis Clinical Quality Assurance representatives, designated agents of Novartis, IRBs/IECs/REBs and regulatory authorities as required.

## **11.3 Informed consent procedures**

Eligible patients may only be included in the study after providing written (witnessed, where required by law or regulation), IRB/IEC/REB-approved informed consent.

Informed consent must be obtained before conducting any study-specific procedures (i.e. all of the procedures described in the protocol). The process of obtaining informed consent should be documented in the patient source documents. The date when a subject's Informed Consent was actually obtained will be captured in their CRFs.

Novartis will provide to investigators, in a separate document, a proposed informed consent form (ICF) that is considered appropriate for this study and complies with the ICH GCP guideline and regulatory requirements. Any changes to this ICF suggested by the investigator

must be agreed to by Novartis before submission to the IRB/IEC/REB, and a copy of the approved version must be provided to the Novartis monitor after IRB/IEC/REB approval.

Women of child bearing potential should be informed that taking the study medication may involve unknown risks to the fetus if pregnancy were to occur during the study and agree that in order to participate in the study they must adhere to the contraception requirement for the duration of the study. If there is any question that the patient will not reliably comply, they should not be entered in the study.

